Phendimetrazine (PHEN), a Schedule III medication under the Controlled Substance Act, is indicated for treating obesity. After oral administration, PHEN is converted to phenmetrazine, which is largely responsible for its behavioral and neuropharmacological effects. Consistent with the notion that compounds with intermediate 5-HT/DA release ratios selectively attenuate the reinforcing effects of COC, phenmetrazine (5-HT/DA ratio = 37) completely eliminated COC-maintained responding in monkeys. Recent research with PHEN has also shown that the parent compound reduces COC self-administration. Moreover, PHEN does not maintain self-administration and produces only limited positive subjective effects compared to d-amphetamine in COC users, which suggests that its abuse potential is low. Although PHEN has yet to be tested as a potential pharmacotherapy for COC dependence in human laboratory experiments or clinical trials to our knowledge, the results of extant preclinical experiments suggest it is a viable option.

In an ongoing study, we have demonstrated that COC can be safely administered to patients maintained on 70, 140 and 210 mg PHEN/day. Whether PHEN attenuates the reinforcing effects of COC, the best predictor for treatment efficacy (Comer et al., 2008; Haney and Spearman, 2008), remains to be determined. **The specific aim of this study is to demonstrate that PHEN maintenance reduces the reinforcing effects of intranasal COC.** To accomplish this aim, we will conduct an experiment in which non-treatment seeking COC-using participants (N=36) will be maintained on doses of PHEN (0 and 210 mg/day [target dose, dose will be titrated up as described below]). The reinforcing and other behavioral effects of intranasal COC (0 [placebo], 20, 40 and 80 mg) will be determined after 7 days of maintenance on the target PHEN dose (i.e., 210 mg/day). In order to monitor the safety of the drug combinations, cardiovascular measures will be taken routinely throughout experimental sessions and subjects will complete a daily side effect scale with nursing staff. We hypothesize that PHEN will attenuate the reinforcing effects of COC, as well as other abuse-related effects of COC (i.e., positive subjective effects). We also hypothesize that COC will be well tolerated during active PHEN maintenance.

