## **4. STUDY POPULATION**

Up to 100 individuals will be screened to participate in this study. We intend to enroll thirty six (24 male and 12 female) completers into the study. These individuals must be English-speaking, English-reading subjects 18-55 years of age of varying ethnic backgrounds and they will be recruited to participate in this five-week experiment. Enrollment in this study will occur between September 1, 2015 and August 31, 2016. Subjects will be required to provide legal proof of age. Subjects must be healthy and without contraindications to COC and PHEN. Subjects must also report recent use of COC and must meet diagnostic criteria for COC abuse or dependence using the Structured Clinical Interview for DSM-IV (SCID). Subjects must provide a COC positive urine during screening to verify COC use status. Screening procedures for all subjects will include a medical history questionnaire, laboratory chemistries (blood chemistry screen, complete blood count, ECG and urinalysis) and a brief psychiatric examination. These procedures will be conducted under our lab's screening protocol (03-0509). Chemistry values and screening outcomes must be deemed normal. If chemistry values or screening outcomes fall outside normal ranges, a study physician must deem them clinically insignificant for a subject to be enrolled. An electrocardiogram must also be within normal limits. Any potential subject with a history of serious physical disease, current physical disease, impaired cardiovascular functioning, chronic obstructive pulmonary disease, history of seizure or current or past histories of serious psychiatric disorder that in the opinion of the study physician would interfere with study participation will be excluded from participation. Subjects with current or past histories of substance abuse or dependence that are deemed by the doctor to interfere with study completion will also be excluded from participation. Female subjects must be using an effective form of birth control (e.g., birth control pills, surgical sterilization, IUD, cervical cap with a spermicide, condoms or abstinence) in order to participate. A urine pregnancy test will be conducted before the start of each experimental session to ensure that female subjects do not continue in the study if pregnant. All study subjects will be judged by the study physician, [name] or [name], M.D. to be healthy.

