Progressive-ratio data (i.e., break point, number of COC doses earned) will be analyzed with two-factor mixed-model ANOVA with COC (within-subject variable; 0 [placebo], 20, 40 and 80 mg), and PHEN (within-subject variable; 0 and 210 mg/day) as the factors. A significant attenuation (i.e., rightward shift in the dose response) of the effects of COC will be inferred if the main effect of PHEN or the interaction of COC and PHEN attains statistical significance in the ANOVA. If the COC-PHEN interaction attains statistical significance, the mean square error term will be used to conduct Tukey's HSD *post-hoc* test to make appropriate pair-wise comparisons between means. Peak-effect and AUC data for the cardiovascular, performance and subjective effects measures obtained during the sampling phase will be analyzed in a similar fashion. Cardiovascular, performance and subjective effects data from the self-administration phase will not be analyzed because participants will likely ingest varying amounts of COC making these data difficult to interpret.

The primary outcome measures for this study are the break point and number of COC doses earned on the progressive-ratio procedure in subjects maintained on active PHEN or placebo. Considering the complete within-subject design, number of dose levels of each drug (i.e., two PHEN conditions and four doses of intranasal COC) enrolling 36 subjects will provide adequate power to detect an effect size ( $d$ ) of at least 0.44 for attenuation of the reinforcing effects of COC as a function of maintenance on PHEN and placebo ( $\text{power} = 0.80$ ,  $\alpha = 0.05$ , G\*Power). We used the results of a previous study conducted in our laboratory to determine an appropriate sample size for the present experiment ([name] et al., 2010). That study demonstrated that d-amphetamine maintenance decreased the reinforcing effects of COC with an estimated effect size ( $d$ ) of approximately 0.46.

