## **17. DATA AND SAFETY MONITORING**

### *Data Monitoring Plan*

Data will be collected using a computerized data collection and management system wherever possible. This system automates the collection of data, which ensures the accuracy and completeness of data collection. The data are stored in a unique file on the hard drive of the computer and are printed after all the tasks are completed. In all instances, the data files do not contain the name of the subject, but instead, each subject is identified by a unique four-digit number. A computer file linking the unique number with the subject's name will be kept on a stand-alone, password-protected computer. All data requiring hand entry (e.g., cardiovascular measures) will be entered by two separate staff members and comparison macros will be run to ensure accuracy. Data files for experimental tasks and physiological measures from each experimental session will be manipulated and combined into a single electronic spreadsheet for each subject by one of the investigators. Data for all subjects will then be combined into a single electronic spreadsheet and separated by experimental measure for statistical analysis using SPSS (IBM, Armonk, NY).

In this protocol the primary outcome measure will be the influence of PHEN maintenance on the reinforcing effects of COC. The alpha level will be set at 5%.

As noted above, wherever possible, data are collected using an automated computer system, which increases the accuracy and completeness of data collection and ensures the validity and integrity of the data. The initial data manipulation described above will be conducted twice and compared. The quality of manipulated data and data analyses will be monitored by random inspection by the PI and/or Co-Investigators.

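### PHEN-versus-placebo comparisons at each COC dose wait on a significant interaction and then use Tukey's HSD, which costs sensitivity for locating the effect by dose but leaves the attenuation conclusion untouched

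*Combined protocol and SAP*

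**What the plan says.** All of this is in the combined protocol and SAP.

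- Section 7, Data Analysis: the progressive-ratio data "will be analyzed with two-factor mixed-model ANOVA with COC" dose (0, 20, 40, 80 mg) and PHEN condition (0, 210 mg/day) as within-subject factors. Attenuation, which the plan glosses as the COC dose-response moving to the right, is concluded if either the PHEN main effect or the interaction is significant.
- The only dose-level rule follows: "If the COC-PHEN interaction attains statistical significance, the mean square error term will be used to conduct Tukey's HSD". These comparisons are labelled post-hoc, and their scope is described no further than as a "test to make appropriate pair-wise comparisons between means". The text does not say which pairs are appropriate, or over how many means the studentized range is taken.
- The primary outcomes are break point and number of COC doses earned. Sampling-phase cardiovascular, performance and subjective measures are to be handled in the same way.
- Section 1 gives the purpose: "The specific aim of this study is to demonstrate that PHEN maintenance reduces the reinforcing effects of intranasal COC". Section 17 (Data Monitoring Plan) sets alpha at 5%.
- Sample size (section 7): 36 subjects and power 0.80 are tied to a standardised difference "of at least 0.44 for attenuation of the reinforcing effects of COC as a function of maintenance on PHEN and placebo". The documents do not say whether d is per dose or averaged over doses, or which SD it uses. Section 4 makes the 36 completers, so no allowance for dropout is needed in the check.

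**The concern.** Two features of the rule work against a dose-level reading. The first is the gate. A 3-df interaction test asks whether the PHEN effect differs between COC doses, so a reduction of similar size at every dose tends to fail it, and then no dose is compared. HSD controls its own family error and does not need the gate. The second is the family. HSD on eight cell means uses the eight-mean studentized range however few pairs are reported, while the comparisons that bear most directly on the specific aim are PHEN against placebo at the same active COC dose.

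What is at stake is the description of the dose-response. Each subject gives eight sessions so that four COC doses are seen under both conditions, and the plan describes attenuation as a shift of the dose-response. A main effect averages over all four doses, placebo included, and cannot show where the change lies.

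**Working it through.** **The plan's own figure.** A two-sided paired t-test with n = 36 and d = 0.44 in paired-SD units gives power 0.728; one-sided gives 0.827. Two-sided power of 0.80 needs 0.480. That follows from 0.44 if d is in raw-SD units and the within-subject correlation is about 0.58: 0.44/√(2 × (1 − 0.58)) = 0.480. Sidedness, type of d and correlation are not stated, so the figure is neither reproduced nor shown to be wrong. It motivates trying both 0.44 and 0.48 below.

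**Critical values.** Means: 2 × 4 = 8. Pairs: 8 × 7/2 = 28. Interaction error df: (4 − 1)(2 − 1)(36 − 1) = 105.

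- HSD, 8 means: q(0.95; 8, 105) = 4.374, so |t| = 4.374/√2 = 3.093, or p = 0.0025 per pair. With 35 or 245 error df, |t| is 3.22 or 3.06, so the choice matters little.
- HSD, 4 means, if that was intended: q = 3.692, |t| = 2.61.
- Bonferroni over three comparisons (the first Holm step) at 105 df: |t| = 2.43.

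**HSD before the gate.** The noncentrality is d × √36. At d = 0.44 this is 2.64, and power is P(T > 3.093) = 33%. It is 38% at 0.46, 50% at about 0.51 and 69% at 0.60. (No subject-by-PHEN variance.)

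**Full procedure.** Simulation of 20,000 trials per row, n = 36, compound symmetry, effects in units of the SD of the paired difference at one dose. Interaction tested by F(3, 105), then HSD over eight means with the interaction mean square. Comparator: ungated paired t-tests at 20, 40 and 80 mg with Holm. Each range runs over subject-by-PHEN variance of 0 and one quarter of residual. The last column is power of the plan's attenuation rule (main effect or interaction).

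| Effect at 0/20/40/80 mg | Gate passed | Gated HSD, given affected dose | Holm over three | Attenuation rule |
|---|---|---|---|---|
| 0/0.44/0.44/0.44 | 45–54% | 20–29% | 64–65% | 93–98% |
| 0/0.48/0.48/0.48 | 52–62% | 27–38% | 74% | 97–99% |
| 0/0.60/0.60/0.60 | 73–83% | 54–68% | 92–93% | about 100% |
| 0.44 at one active dose only | 44–54% | 28–38% | 55–56% | 58–62% |
| 0.44 at all four | 5% | 2–3% | 64–65% | 98–100% |

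Monte Carlo error is at most √(0.25/20,000) = 0.35 percentage points.

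In the last row the main effect is significant and the interaction is not in about 93–95% of trials, so the trial concludes attenuation and compares no dose.

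**How much is gate and how much is family.** At 0.48 on the three active doses, removing only the gate raises HSD from 27–38% to 42–55%. Keeping the gate and using four means gives 36–47%. Neither change alone reaches Holm's 74%.

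**The case against.** The strongest reply is that the trial's conclusion does not use these comparisons. Attenuation follows from the main effect or the interaction, and the last column of the table shows that this rule performs well when PHEN acts at all active doses. No section states finding the dose as an aim; sections 1 and 2 ask whether PHEN maintenance reduces the reinforcing effects of COC. With no interaction, the marginal effect is the usual summary. All of this stands, and it limits the point to a secondary loss.

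Three further objections stand in part.

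- **The family is not stated.** A reader might infer that the plan commits to testing all 28 pairs. It says only that appropriate comparisons will be made. The 3.09 follows if HSD is applied to the eight cell means; with four means it is 2.61. Reporting fewer pairs does not lower it.
- **The detection rates depend on assumed effects.** A reader might infer that a real dose-level reduction is usually missed. That holds at 0.44 to 0.48 per dose, but not at about 0.60 when the effect is the same at all active doses. The documents give no per-dose effect; if 0.44 is an average over doses, some per-dose effects may be smaller and missed more often.
- **The comparison is not purely one of gate and family.** HSD uses the pooled interaction mean square, which excludes subject-by-PHEN variance; the paired tests use each dose's own SD. That difference drives the spread within the gated HSD column. Holm also does best when all three doses are affected; with one dose affected the gap narrows to 28–38% against 55–56%.

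Nor are matched-dose pairs the only useful ones. Active COC against 0 mg within a condition also bears on a shift of the dose-response, and the COC main effect, averaged over PHEN conditions, does not replace it.

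**Conclusion.** The point holds as one about locating the effect by COC dose. The written rule is markedly less sensitive for that than three planned matched-dose comparisons: about 20–29% against 64–65% at 0.44, and 54–68% against 92–93% at 0.60, with equal effects at the active doses. Under an even reduction at all four doses it almost always yields no dose comparison.

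These figures rest on d read as a per-dose effect in paired-SD units, 36 completers, compound symmetry and HSD over eight means. Part of the miss rate comes from the sample size: at 0.44 an unadjusted two-sided paired test has only 73% power.

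A reader might infer that the primary test is underpowered because of this rule, or that a positive trial could be turned negative by it. The documents do not support either, because no pairwise test enters the attenuation decision.

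**What to change.** In section 7, Data Analysis, add a sentence for both primary outcomes (break point and number of COC doses earned). Pre-specify three paired PHEN-versus-placebo comparisons, at 20, 40 and 80 mg COC, Holm-adjusted within each outcome. Report each with its estimate and 95% CI whether or not the interaction is significant. State that they locate the effect by dose and add no further route to the attenuation conclusion, which stays with the main effect or the interaction.

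Keep the interaction-gated Tukey HSD for the remaining pairs, such as active COC against 0 mg within a maintenance condition, as secondary post-hoc comparisons, and state the number of means over which the studentized range is taken.

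The cost is the added text; no subjects, sessions or data are needed. The downside is that the planned contrasts and the remaining Tukey pairs become separate families, so error is controlled within each but not across both. The plan should say so.

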## **9. POTENTIAL RISKS**

The self-administration measure, subjective drug-effect questionnaires, performance and physiological measures employed in these studies are benign. The risks to the study subjects are those related to the ingestion of the drugs under study. All of the drugs to be administered in the proposed research are commercially available. The relative safety as well as the contraindications and possible side effects of these compounds are well known and documented. However, the administration of any drug involves some risks simply because individuals differ in their reactions to drugs. The main risk is that subjects will experience side effects that may be unpleasant.

Common side effects of COC and PHEN include nervousness, restlessness, faintness, irritability, shaking, nausea, headache, flushing, increased urine production, sweating, performance impairment, rash, blurred vision, irritation in nose and throat (due to intranasal insufflation of COC only), difficulty sleeping, loss of appetite, weight change and changes in heart rate or blood pressure. More serious side effects following the chronic, unsupervised administration of much higher doses of cocaine have occurred and include arrhythmias, psychotic episodes, suppressed breathing, seizures, myocardial infarctions, heart failure and death.

These side effects may be more frequent and larger in magnitude when testing the COC-PHEN combinations.

The doses to be administered in the present experiment were chosen to minimize, if not eliminate, the chance of these side effects occurring since these side effects are related to dose. Thus, it is unlikely that subjects will experience side effects during the experimental protocol. All sessions proposed in this application will be conducted at the CRIU and under medical supervision. Side effects of the drugs are temporary, usually dissipating in less than 24 hours. The principal investigator on this project, [name], has had extensive experience over the last 15 years administering therapeutic and supratherapeutic doses of stimulant drugs to subjects in both inpatient and outpatient settings and has never observed a serious, unexpected adverse effect. [name] will train all staff on this project.

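### For heart rate and blood pressure the plan gives no ungated PHEN-versus-placebo estimate with an interval at each COC dose, so a moderate rise confined to 80 mg would often not be localized

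*Combined protocol and SAP*

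**What the plan says.** Section 7 (Data Analysis) sets out a two-factor within-subject ANOVA for the progressive-ratio outcomes, with four COC doses and two PHEN conditions. An effect of PHEN is inferred if either the PHEN main effect or the COC-PHEN interaction is significant. Pairwise comparisons by Tukey's HSD follow only if the interaction is significant, and the comparisons in the family are not listed.

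The safety-related measures take the same route: "Peak-effect and AUC data for the cardiovascular, performance and subjective effects measures obtained during the sampling phase will be analyzed in a similar fashion". Cardiovascular data from the self-administration phase are not analyzed, so this is the only group-level cardiovascular comparison that the plan specifies.

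Two other places give these measures a safety role. Section 1 (Background) says that they are taken to monitor the safety of the combination, and adds: "We also hypothesize that COC will be well tolerated during active PHEN maintenance". Section 9 (Potential Risks) lists changes in heart rate and blood pressure among the side effects and warns: "These side effects may be more frequent and larger in magnitude when testing the COC-PHEN combinations". The plan names no margin, interval or dose-level contrast by which the tolerability hypothesis would be judged at group level.

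**The concern.** An interaction gate followed by family-wise control is built to limit false positives. That suits a claim of benefit. For a possible harm the costlier error is failing to see it, and a tolerability statement says that no important rise exists. A non-significant test cannot support such a statement, whereas an interval can.

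The combined exposure is highest at 80 mg COC on active PHEN. Under the plan, a PHEN-versus-placebo result at that dose appears only if the interaction is significant. Otherwise the reader gets at most a difference averaged over placebo, 20, 40 and 80 mg. At stake is whether the trial can say how much PHEN raises heart rate or pressure at the top dose, and how large a rise its data leave open.

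**Working it through.** **Inputs.** From section 7: n = 36, a 4 × 2 within-subject layout ("within-subject variable; 0 [placebo], 20, 40 and 80 mg), and PHEN (within-subject variable; 0 and 210 mg/day) as the factors"), significance at 0.05. The documents give no cardiovascular SD or effect size. Assumed: d, the PHEN-minus-placebo difference at 80 mg in SDs of the paired difference, is 0.44 (borrowed from the efficacy statement) to 0.48 (the value an ungated paired test detects with 80% power at n = 36); subject-by-PHEN variance is 0 to one quarter of residual; there are 36 complete cases; sphericity holds; the Tukey family is all 8 means.

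**The plan's own figure.** Section 7 says that "enrolling 36 subjects will provide adequate power to detect an effect size" "of at least 0.44 for attenuation of the reinforcing effects of COC", with power 0.80. As a paired t test with d = 0.44, 36 subjects give power 0.83 one-sided (34 needed) and 0.73 two-sided (43 needed). A repeated-measures calculation with f = 0.22 and two measurements gives 0.80 if the unstated correlation is 0.58. So the figure is reproduced to within two subjects one-sided, or with an assumed correlation. It covers the reinforcing effect only, not the cardiovascular measures.

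**Ungated contrast at 80 mg.** Noncentrality = d√36 = 6d, with 35 df.
- d = 0.44: 2.64, power 0.73.
- d = 0.48: 2.88, power 0.80.
- 95% CI half-width: 2.030/6 = 0.34 SD of the paired difference.

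**PHEN main effect.** It tests the mean of four paired differences. With no subject-by-PHEN variance, the SD of that mean is 1/√4 = 0.5. With a ratio of one quarter, the shared part is 0.25/1.25 = 0.2 of the paired-difference variance, so the SD is √(0.2 + 0.8/4) = 0.632.
- Equal rise at all doses, d = 0.44: noncentrality 6 × 0.44/0.5 = 5.28 or 6 × 0.44/0.632 = 4.17; power 0.999 or 0.98.
- Rise at 80 mg only, d = 0.44: the averaged effect is 0.44/4 = 0.11; noncentrality 1.32 or 1.04; power 0.25 or 0.17.

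**Interaction gate, rise at 80 mg only.** λ = 36 × 0.75 × d² / v with 3 and 105 df, where v is 1 or 0.8. For d = 0.44, λ = 5.23 or 6.53, and power is 0.44 or 0.54.

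**Tukey step.** q(0.95; 8 means, 105 df) = 4.374, so |t| must exceed 4.374/√2 = 3.09, a per-pair p of about 0.0025.

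**Combined rule, by simulation, rise at 80 mg only** (where two figures stand, repeat runs differed by that much):

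| d | Subject-by-PHEN / residual | Gate opens | Gate + Tukey at 80 mg | Main effect | Tukey or main effect | Ungated contrast |
|---|---|---|---|---|---|---|
| 0.44 | 0 | 0.44 | 0.28–0.29 | 0.25 | 0.43–0.44 | 0.73 |
| 0.44 | 1/4 | 0.54 | 0.37 | 0.17 | 0.45 | 0.73 |
| 0.48 | 0 | 0.52 | 0.36–0.37 | 0.29 | 0.51–0.52 | 0.80 |
| 0.48 | 1/4 | 0.62 | 0.46–0.47 | 0.20 | 0.54–0.55 | 0.80 |

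At least one of the two omnibus tests is significant in 0.59 to 0.69 of trials across these settings.

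**Other patterns and sizes.**
- Rise graded with COC dose (0, 1/4, 1/2 and all of d), d = 0.48: Tukey or main effect 0.64 to 0.75.
- Equal rise at all doses: the gate opens in about 0.05 of trials, which is simply the type I rate for an interaction that is not there.
- Rise at 80 mg only, gate plus Tukey: 50% is reached at about d = 0.54 with no subject-by-PHEN variance, and at a somewhat smaller d with it. At d = 0.60 the figure is 0.63 to 0.74, and at d = 0.80 it is 0.92 to 0.96.

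**The case against.** A reader might infer that a PHEN-related rise at the top COC dose is more likely to be missed than found. The documents do not support that in general. The PHEN main effect is an ungated part of the decision rule. Counting it, the plan flags an 80-mg-only rise of d = 0.48 slightly more often than not, and larger rises mostly. With no cardiovascular SD or effect size in the documents, no single d can be presented as the expected one.

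A reader might also infer that an additive rise (PHEN plus COC, no interaction) goes unseen. The reverse is true: it is what the main effect tests, and the averaged difference then equals the difference at every dose.

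Third, the contrast of 73–80% with 28–46% mixes error rates. With a Bonferroni correction over four doses, the ungated contrast at d = 0.44 has power 0.51. So about half of the gap between 0.73 and 0.29 comes from the looser alpha. The all-means Tukey family is also an assumption, because section 7 leaves the choice of comparisons open.

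Fourth, nothing in the documents says that a non-significant ANOVA will be read as good tolerability. Section 7 has vital-sign limits for dosing and removal, ECG monitoring and a daily side-effect scale, and section 17 has adverse-event review. Nor does the plan forbid descriptive intervals.

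All four points stand, and they limit the concern. They do not supply an estimate at 80 mg. A significant main effect is an average over doses, and individual limits protect subjects without measuring the group-level rise.

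**Conclusion.** The concern holds in a limited form. The planned route detects a rise common to all COC doses well. It is weak at localizing a moderate rise confined to 80 mg: about 28–46% by the gated comparison, and about 43–54% flagged by Tukey or the main effect, against 73–80% for an ungated contrast. These figures rest on the assumed d of 0.44 to 0.48, subject-by-PHEN variance of 0 to one quarter of residual, a Tukey family of all 8 means and 36 complete cases. Removal of subjects who exceed the vital-sign limits was not modelled.

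The part that depends on none of these assumptions is that no planned interval shows how large a rise at 80 mg, or at any other COC dose, the data leave open. The tolerability hypothesis therefore has no stated group-level criterion. This does not affect the efficacy analysis or the sample size.

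**What to change.** Keep the ANOVA as written. For peak heart rate, systolic pressure and diastolic pressure in the sampling phase, add that the PHEN-minus-placebo mean difference at each COC dose will be reported with an unadjusted 95% confidence interval, whatever the interaction result. State that any group-level tolerability statement will be supported by these intervals, alongside the adverse-event, UKU and vital-sign-limit data, and not by non-significance.

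The cost is one table of 3 × 4 = 12 intervals from data already collected, plus a sentence or two in Data Analysis. No subjects are added; powering the interaction itself at 0.80 for an 80-mg-only d of 0.44 would need 77. The downside is that some intervals will exclude zero by chance: 12 × 0.05 = 0.6 expected if PHEN has no effect. That is acceptable for a safety description, provided that the table is labelled as unadjusted.
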